# 4. Liver function monitoring visit

Liver Function monitoring visit	Time	Note
Medical History	2	PRA
Concomitant Medications	2	PRA
Adverse Events (b) and drug abuse related AEs	3	PRA
Anxiety short form	2	Study subject
Depression short form	2	Study subject
Emotional and behavioral dyscontrol short form	2	Study subject
SCOPA-sleep	4	Study subject
EQ-5D	2	Study subject
C-SSRS	2	PRA
Vitals	5	PRA
Blood draw for liver function tests	10	CTRC
Total visiting time	36	0.5 hours

2.5 mg/kg/day Dose assessment visit	Time	Note
Vital Signs, orthostatic BP	10	PRA, Begore taking study drug
Taking study drug in clinic	2	Study subject
Cognitive assessment battery	60	PRA
Vital Signs, orthostatic BP	10	PRA, one hours after taking study drug
Medical History	2	PI, PRA
Concomitant Medications	2	PI, PRA
Adverse Events and drug abuse related AEs Withdrawal AEs and liver function related AEs	3	PI, PRA
Complete Physical Exam	10	PI
Neurological exam	10	PI
QUIP-RS	5	PI
CGI	1	PI
MDS-UPDRS (all 4 parts), H&Y, Schwab & England Activities of Daily Living Scale	30	PI, Study subject
Unified Dyskinesia Rating Scale (UDysRS)	5	PI, Study subject
MOCA	10	PRA
TUG	5	PRA
NMSS	10	PRA
Home diary collection and review	2	PRA
Tremor constancy and amplitude measure (k)	5	PRA, 2 hours after taking study drug
PSG equipment and data collected (u)	2	PRA
Blinding assessment	1	PRA
Study drug compliance check	2	PRA
C-SSRS	2	PRA
RBDSQ	2	PRA
NPI	5	
Anxiety short form	2	Study subject
Depression short form	2	Study subject
Emotional and behavioral dyscontrol short form	2	Study subject
SCOPA-sleep	5	Study subject
Insomnia Severity Index (ISI)	2	Study subject
Modified Dysfunctional Beliefs and Attitudes about Sleep Questionnaire (DBAS-16)	3	Study subject
Pittsburgh Sleep Quality Index	3	Study subject
IRLS	2	Study subject
Fatigue severity scale	3	Study subject

5. 2.5 mg/kg/day Dose assessment visit

Pain intensity and interference short form	2	Study subject
Bladder function-OABSS	3	Study subject
PDQ-39	5	Study subject
EQ-5D	2	Study subject
PGI-I	1	Study subject
PGI-C	1	Study subject
Urinalysis, pregnancy test if applicable	5	PRA
Urinary collected for CBD and metabolites levels test	2	PRA
Take picture of central face	5	PRA, Study subject
ECG (12-LEAD)	10	CTRC
Blood draw for Hematology, CMP, cannabis test	10	CTRC, 3 hours after taking study drug
Vital Signs, orthostatic BP	10	PRA, 3 hours after taking study drug
Total visiting time	275	4 hours

6.Safety follow up visit		
Safety follow up visit	Time	Note
Medical History	2	PI, PRA
Concomitant Medications	2	PI, PRA
Adverse Events and drug abuse related AEs Withdrawal AEs, and liver function related AEs	3	PI, PRA
QUIP-RS	10	PI
Complete Physical Exam	10	PI
Unified Dyskinesia Rating Scale (UDysRS)	5	PI, Study subject
MDS-UPDRS (all 4 parts), H&Y, Schwab & England Activities of Daily Living Scale	30	PI, Study subject
Vital Signs, orthostatic BP	10	PRA
Urinalysis if applicable	5	PRA
Urinary CBD and metabolites levels test	5	PRA
NMSS	10	PRA
Urine Pregnancy Test (for women childbearing potential)	5	PRA
MOCA	7	PRA
C-SSRS	2	PRA
RBDSQ	2	Study subject
NPI	5	
Anxiety short form	2	Study subject
Depression short form	2	Study subject
Emotional and behavioral dyscontrol short form	2	Study subject
SCOPA-sleep	5	Study subject
IRLS	2	Study subject
Fatigue severity scale	5	Study subject
Pain intensity and interference short form	2	Study subject
Bladder function-OABSS	3	Study subject
PDQ-39	5	Study subject
EQ-5D	2	Study subject
Blood draw for Hematology, CMP, Cannabis test	10	CTRC
ECG (12-LEAD)	10	CTRC
Total visiting time	165	3 hours

Appendix 7: Chemotherapeutic, antihistaminic and Anti0inflammatory medications, including, but not limited to:

Alemtuzumab (Lemtrada) Aspirin Celecoxib (Celebrex) Daclizumab (Zinbryta) Diclofenac (Cambia, Cataflam, Voltaren-SR, Zipsor, Zorvolex) Diflunisal (Dolobid) Dimethyl fumarate (Tecfidera) Etodolac (Lodine) Fingolimod (Gilenya) Glatiramer acetate (Copaxone) Ibuprofen (Motrin, Advil) Indomethacin (Indocin) Interferon beta-1a (Avonex, Rebif) Interferon beta-1b (Betaseron, Extavia) Ketoprofen (Active-Ketoprofen) Ketorolac (Toradol) Mitoxantrone Nabumetone (Relafen) Naproxen (Aleve, Anaprox, Naprelan, Naprosyn) Natalizumab (Tysabril) Ocrelizumab Oxaprozin (Daypro) Peginterferon beta-1a (Plegridy) Piroxicam (Feldene) Rituximab (Rituxab) Salsalate (Disalsate) Sulindac (Clinoril) Teriflunomide (Aubagio) Tolmetin (Tolectin) Other chemotherapeutic, antihistaminic and anit-inflammatory medications per PI discretion

Inflammatory Diseases	Cryoglobulinemia
Gout	Allergic asthma
Lupus	Anaphylaxis
Asthma	Angioedema
Crohn's disease	Urticaria
Eczema	Latex allergies
Ulcerative colitis	Systemic lupus erythematosus
Hepatitis	Acute hypersensitivity pneumonitis
Nephritis, Glomerulonephritis	Leukocytoclastic vasculitis
Psoriasis	
Vasculitis	Other inflammatory and atopic disease per PI
	discretion
Thyroiditis	
Sarcoidosis	
Multiple Sclerosis	
Rheumatoid and other inflammatory arthritides	
Seborrheic dermatitis	
Wegener's granulomatosis	

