We considered other factors while choosing a study drug to use in the randomized controlled parallel study. While Epidiolex® was the best option for our open label dose-escalation study, we recognized that a disadvantage of using a pure CBD preparation and such a high dose is that it is different from what persons with PD obtain from local dispensaries. While local dispensaries sell cannabis that is

high in CBD, their products are not pure CBD and markedly lower doses are used, so our findings would not be very applicable to the products our PD patients are taking. The study drug and dosage to be used in the randomized controlled parallel study will be more similar to what persons with PD are obtaining from local dispensaries. Another consideration is that THC, CBD, and the other components of the cannabis plant interact, e.g., the "entourage" effect, and this interaction may have a meaningful effect, which would not be occurring in Epidiolex® since it is such a pure CBD product.

Therefore, we will use a cannabis extract with 59.3% CBD and 1.96% THC (30:1 CBD:THC) from NIDA. We will give 1.25 mg/kg twice daily of CBD and 0.041 mg/kg twice daily of THC. This equals 2.11 mg/kg twice daily (4.22 mg/kg/day) of the NIDA extract. For our average sized PD participant (84 kg) in our prior trial this will be approximately 100 mg CBD and 3.3 mg THC twice daily (morning and evening - > 6 hours apart). Therefore, the THC dose is below the threshold, ~5mg, that is expected to cause a person to feel "high." The interval of >6 hours is to minimize the possibility of the THC effect to overlap/build up. The extract solution will be in a sesame oil formulation, 100 mg/ml of CBD, so the participant would ingest 1 ml (100 mg CBD) twice daily. This much smaller amount of CBD and of oil is expected to be better tolerated, including less likely to cause liver enzyme elevations, than the study drug in the open label study.

In comparison to the open label study, the amount of CBD in this study is less than 15% (19.23/2.5). This dose and the fact that there is a small amount of THC is in the product makes this study drug more similar to what persons are receiving from local dispensaries, although it may generally have a higher in CBD content. Therefore, the results of the study using this product will be more generalizable to the Colorado PD population.

Whether participants should be allowed to drive has been carefully considered:

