- To help the participant understand how the study drug affects them we will monitor them in clinic. A validated Alertness Scale will be administered before the dose and again when the blood level is expected to reach peak in three hours.
- We will have the following language in the consent form and will emphasize it verbally: "Whether or not the study drug affects driving ability is not known. You should not drive or operate heavy machinery while taking study drug."

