photography) will be done. Alertness test (Stanford Sleepiness Scale) will be done before and three hours after the first dosing was administered at clinic. Tremor evaluations reviewed. Home diary is also dispensed. Participants will pick up PSG equipment and home sleep test instruction and do the home sleep test for up to 14 to three nights before the baseline visit. Participants will complete Morning Daytime Dysfunction questionnaire and sleep diary on the morning after the sleep test. PSG equipment and data collected before or at this visit. Participants take the first dose and are instructed on how to take the medication and how to fill out the diary at home. Participants will be monitored for 2 hours and vital signs and orthostatic blood pressures will be checked at one hour after taking the study drug. Participants are also told to bring in empty, partially used, and unused bottles of study drug at next clinical visit. Participants will be told not to take the study drug on the day of the next visit, as they will take it upon arrival under instruction by study staff. Participants will be given two urine cups, 100 mL each, and will be instructed to collect their urine the morning of the 1.25 mg/kg/day assessment visit. They are asked to fill each cup at least three-quarters full, if possible, and to bring them to the visit (no refrigeration needed). Participants are instructed to measure their tremors at home for three days prior to each dose assessment visit.

Part of the above procedures can be done remotely through Zoom or other HIPAA-compliant platform, between screening and onsite baseline visit: Eligibility confirmation, medical history, concomitant medications collection, NMSS, OABSS, Anxiety short form, Depression short form, SCOPA-Sleep, ISI, DBAS-16, Pittsburgh Sleep Quality Index, Dermatology Intake Form, DLQI, Alertness test, RBDSQ, C-SSRS, IRLS, Fatigue severity scale, Pain intensity and interference short form, PDQ-39, EQ-5D.

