Visit 3 (3-4 days, 1.25 mg/kg/day) and Visit 4 (14 (+4) days, 2.5 mg/kg/day), dose assessment visits: On the morning of the visits, participants will collect their urine and bring it to the visits. Study coordinator will collect and store the urine cups in a -80°C freezer until shipment for urinary CBD and metabolites test. Concomitant medications, change in medical history, vital signs, orthostatic blood pressures, complete physical exam, detailed neurological exam, MDS-UPDRS, UDysRS, H&Y rating, tremor constancy and amplitude, NMSS, TUG, Anxiety short form, Depression short form, Emotional and behavioral dyscontrol short form, Fatigue Severity Scale, Pain Intensity and Interference short form, MoCA, RBDSQ, QUIP-RS, C-SSRS, NPI, SCOPA-sleep, ISI, DBAS-16, Pittsburgh Sleep Quality Index, IRLS, OABSS, EQ-5D, PDQ-39, CGI, PGI, blood draw for safety labs (hematology, Complete Metabolic Profile and Liver Function Tests) and blood cannabis analysis, urinalysis, ECG, and urine pregnancy test are done. Study drug compliance check, adverse event check and blinding assessment are done. Participants will take their study drug upon their arrival to the clinic and record the taking time. Blood is drawn for cannabis testing and safety labs three hours after the dose. Participants will be monitored and vital signs and orthostatic blood pressures will be checked at one and three hours (2.5 mg/kg/day dose assessment visit) after taking the study drug. Home diary is collected and reviewed. Urine cups dispensed. In addition to the procedures above, for Visit 3 (3-4 days, 1.25 mg/kg/day), participants are told to bring in empty, partially used, and unused bottles of study drug at next clinical visit. Participants will be told not to take the study drug on the day of the next visit, as they will take it upon arrival under instruction by study staff. Participants are instructed to measure their tremors at home for three days prior to 2.5 mg/kg/day dose assessment visit. Participants will be given the questionnaires of SCOPA-sleep, Anxiety short form, Depression short form, Emotional and behavioral dyscontrol short form, EQ-5D-5L, C-SSRS. Study staff will call the participants on the 3rd to 5th day on 2.5 mg/kg/day to remind them to complete the questionnaires and bring it in at next clinic visit.

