# 2. Baseline visit

Baseline visit	Time	Note
Eligibility Criteria	1	PRA, PI
Medical History	2	PRA, PI
Concomitant Medications	2	PRA, PI
Randomization	1	PRA, PI
Alertness test	3	Study subject, before taking study drug
Vital Signs, orthostatic BP, height, weight	10	PRA, before taking study drug
Taking study drug	2	Study subject
Dispense study drug and instruction	10	PI
Adverse Events (b)	2	PRA, PI
Brief physcial exam (heart and lung ausculation)	5	PI
CGI	1	PI
MDS-UPDRS (all 4 parts), H&Y, Schwab & England Activities of Daily Living Scale	30	PI, Study subject
Unified Dyskinesia Rating Scale (UDysRS)	5	PI, Study subject
Vital Signs, orthostatic BP	10	PRA, one hour after taking study drug
Cognitive assessment battery	60	PRA
C-SSRS	2	PRA
NMSS	10	PRA
Home diary dispense and instruction	3	PRA
Tremor measure device dispatched and instruction	5	PRA
RBDSQ	2	Study subject
Anxiety short form	2	Study subject
Depression short form	2	Study subject
SCOPA-sleep	5	Study subject
Insomnia Severity Index (ISI)	2	Study subject
Modified Dysfunctional Beliefs and Attitudes about Sleep Questionnaire (DBAS-16)	3	Study subject
Pittsburgh Sleep Quality Index	3	Study subject
IRLS	2	Study subject
Fatigue severity scale	3	Study subject
Pain intensity and interference short form	2	Study subject
Bladder function-OABSS	3	Study subject
PDQ-39	7	Study subject
EQ-5D	2	Study subject

PGI-I	1	Study subject
Take picture of central face	5	PRA, Study subject
TUG	5	PRA, Study subject
Urine drug (THC) test, urine pregnancy test if applicable	5	PRA
Urine cups dispense and urine collection instruction	2	PRA
Tremor constancy and amplitude measure	5	PRA, 2 hours after taking study drug
Alertness test	3	Study subject, 3 hours after taking study drug
PSG equipment and data collected	2	PRA
Total time	230	estimated visiting time-3.5 hours

3. 1.25 mg/kg/day dose assessment visit

1.25 mg/kg/day dose assessment visit	Time	Note
Vital Signs, orthostatic BP	10	PRA, Begore taking study drug
Taking study drug in clinic	2	Study subject
Vital Signs, orthostatic BP	10	PRA, one hours after taking study drug
Medical History	2	PI, PRA
Concomitant Medications	2	PI, PRA
Adverse Events and drug abuse related AEs	2	
Withdrawal AEs, Liver function related AEs	3	PI, PRA
Complete Physical Exam	10	PI
Neurological exam	10	PI
QUIP-RS	5	PI
CGI	1	PI
MDS-UPDRS (all 4 parts), H&Y, Schwab &		
England Activities of Daily Living Scale	30	PI, Study subject
Unified Dyskinesia Rating Scale (UDysRS)	5	PI, Study subject
MOCA	10	PRA

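### The baseline cognitive battery is listed after the first dose, and at a different post-dose time from the 2.5 mg/kg/day battery, so its change score can understate acute cognitive harm

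*Combined protocol and SAP*

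**What the plan says.** **Dosing in clinic.** At the baseline visit, "Participants take the first dose and are instructed on how to take the medication" (Section IV.C.1, Visit 2). At the dose assessment visits, "Participants will take their study drug upon their arrival to the clinic and record the taking time".

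**Place of the battery.** Appendix 6 gives the same row, "Cognitive assessment battery 60 PRA", in two lists. In list 2 (baseline visit) it comes after dosing and after the vital signs labelled "PRA, one hour after taking study drug". In list 5 (2.5 mg/kg/day visit) it comes directly after dosing and before the vital signs labelled "PRA, one hours after taking study drug". At baseline the first alertness test and the first vital signs are marked as pre-dose; the battery is not.

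**Text.** The Visit 2 and Visit 4 descriptions require the full battery but give no time relative to the dose. Other measures do have one: tremor at two hours, vital signs at one and three hours, and "Blood is drawn for cannabis testing and safety labs three hours after the dose". Alertness is tested before the first dose and "again when the blood level is expected to reach peak in three hours" (Section III).

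**Analysis.** Section IV.A item 1.4 makes cognition a safety outcome compared as change from baseline, and the same tools serve as exploratory efficacy outcomes. Section IV.F tests the change scores between arms with a two-sample t-test.

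**The concern.** A baseline value should be free of treatment. Here the row order puts it one to two hours after the first dose, following randomisation. Placebo participants have received no active drug at that point and CBD participants have, so randomisation does not cancel a first-dose effect; it becomes part of the between-arm difference in change. Baseline adjustment in a regression model would not repair this, because the covariate is itself measured after treatment.

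The second battery is also at a different, earlier time after its dose. The two measurements therefore differ in accumulated exposure and in position on the dose curve.

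The background section names cognitive impairment as a THC risk. A null or favourable difference on the battery could be read as cognitive safety when part of an acute effect had been subtracted. The full battery is scheduled only at these two visits, so no other battery value can restore the comparison.

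**Working it through.** **1. The plan's own totals.** The baseline rows of Appendix 6 sum to 230 min (stated 230). The 2.5 mg/kg/day rows sum to 276 min (stated 275).

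**2. Post-dose times in row order** (minutes from the start of the dosing row):

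- Baseline: dosing 2 + intervening rows (10 + 2 + 5 + 1 + 30 + 5 = 53) = 55, where the one-hour vital signs begin; + 10 = 65, battery start; + 60 = 125, battery end. If the vital signs start at exactly 60 min, the window is 70 to 130.
- 2.5 mg/kg/day visit: dosing 2, battery 2 to 62, one-hour vital signs at 62.

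In both lists the one-hour vital signs fall close to one hour, so this stretch reads as a sequence.

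**3. Could the baseline battery be before the dose anyway?** This check does not use row order. The second alertness test is 180 min after the dose, so a 230-min visit leaves at most 230 − 180 = 50 min before dosing. With the appendix's estimate of 3.5 hours, it leaves 210 − 180 = 30 min. The rows already listed before dosing take 1 + 2 + 2 + 1 + 3 + 10 = 19 min. A 60-min battery does not fit, provided the visit runs to its stated length.

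**4. What the analysis estimates.** Let d1 be the effect of the first dose on the baseline battery and d2 the effect at the later battery, both in the CBD arm and zero on placebo. Then:

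difference in change = (d2 − d1) − 0 = d2 − d1; share of d2 retained = 1 − d1/d2.

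| d1/d2 (assumed) | share of d2 retained |
|---|---|
| 0 | 100% |
| 0.25 | 75% |
| 0.5 | 50% |
| 1 | 0% |
| above 1 | sign reversed |

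The documents give neither d1 nor d2.

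**5. Exposure, as an illustration only.** Assume a one-compartment oral model, C(t) = ka/(ka − ke) × (e^(−ke·t) − e^(−ka·t)), with the peak at the stated 3 h and the CBD half-life of 2 to 5 days from Section II. This gives ka = 1.579 and 1.946 per hour. Doses are four once-daily, then nine full twice-daily days with the evening dose 10 h after the morning one. Windows are 70 to 130 min at baseline and 0 to 60 min later.

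- Increment from that day's dose, as a share of its own peak: CBD 0.95 to 0.96 at baseline, 0.52 to 0.57 at the later visit.
- THC has no stated kinetics. With an assumed peak time of 1 to 3 h and half-life of 1.5 to 6 h: 0.86 to 0.98 at baseline, 0.36 to 0.78 later.
- Total CBD goes the other way. The carried-over level before the later dose is 5.33 (2-day half-life) or 10.91 (5-day) single-dose peaks. The total relative to the baseline window is therefore (5.33 + 0.516)/0.945 ≈ 6 to (10.91 + 0.567)/0.964 ≈ 12 times.

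Only the acute increment is lower at the later visit; accumulated CBD is far higher.

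**The case against.** **Row order is not a timetable.** Appendix 6 is a list of procedures and durations, and some of its own labels break the order. The two-hour tremor row would fall at 201 min at baseline and 167 min at the 2.5 mg/kg/day visit. The one-hour vital signs at the 1.25 mg/kg/day visit directly follow the 2-minute dosing row. The baseline urine THC test would fall at 194 min after a THC-containing dose, although a positive result is a screen failure. This stands as a limit on the exact minutes. It does not rescue the baseline battery, because step 3 shows no room for it before the dose within the stated visit length. If sites ignore the list, the timing is simply uncontrolled.

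**Cognition is covered elsewhere.** MoCA is done at screening before any drug and at both dose visits, at about 140 min post-dose in row order at the later one. Abuse-related adverse event terms include impaired attention and cognition. This stands in part: MoCA is a brief screen and does not replace the battery.

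**Testing after ten or more days can target steady state.** That is a legitimate aim and supports the later visit as such. It does not justify a post-dose baseline.

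**Stronger readings that the documents do not support.** A reader might infer that the protocol's own figures put the drug effect at its lowest in the first hour. They do not: the only figure is a three-hour peak in blood level, with no effect curve and no THC peak time or half-life. The statement "The interval of >6 hours is to minimize the possibility of the THC effect to overlap/build up" gives a reason for the dosing interval; it does not say the effect has gone by then. A reader might also attach a percentage of lost effect by drawing a curve up to the peak, but the result depends on the assumed shape. Nor is a reversed result shown, since it needs d1 greater than d2.

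**Conclusion.** The concern holds for the acute component of any cognitive effect. The baseline battery is placed after the first dose, the two batteries are at unmatched post-dose times, and the text fixes neither. The between-arm difference in change estimates d2 − d1, so a harmful first-dose effect understates harm by d1. Its size cannot be derived from the documents.

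This rests on two assumptions: that the baseline visit keeps roughly to its stated length, and that the first dose has some effect on test performance within about two hours. If the first dose has no such effect, the post-dose baseline introduces no bias. The effect of accumulated CBD is still captured. The primary outcome is not the subject of this point. The plan should be changed because the defect affects a named safety outcome and a schedule change removes it.

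**What to change.** **Baseline.** In Appendix 6 list 2 and the Visit 2 text, place the battery before the first dose.

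**2.5 mg/kg/day visit.** In list 5 and the Visit 4 text, state one fixed post-dose time for the battery, preferably within two to three hours, near the expected blood peak. Keep MDS-UPDRS Part III at its present post-dose time (about 105 min in row order), so that the primary outcome is not moved.

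One arrangement that fits: fill the first hour with the self-completed forms (38 min) and MDS-UPDRS Parts I, II and IV. Those parts take about 20 min, if Part III with the two staging scales takes the 10 min listed at screening out of the 30-min row. That is 58 min in place of the 60-min battery, so Part III stays at about 105 to 115 min. Tremor follows at 120 to 125 and the battery at 125 to 185. The three-hour blood draw then needs a tolerance of a few minutes.

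**Cost.** The later visit need not lengthen. The baseline visit does: 19 + 60 min before the dose, 180 min to the alertness test, then 3 + 2 min, gives 264 min. That is 34 min above the stated 230 and 54 above the 3.5-hour estimate. If the 5-min urine tests also precede the dose, the increase is 39 to 59 min. Completing forms remotely offsets little, because the three-hour wait stays: the remaining dosing and post-dose rows total 230 − 19 − 60 = 151 min, already less than 180.
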